5.2 Study Materials

The following materials will be provided at study start:

- Protocol and appendices;
- NCI CTCAE version 4.0;
- Nivolumab Investigator Brochure;
- Ipilimumab Investigator Brochure;
- Laboratory kits, shipping materials;
- Laboratory manuals for collection and handling of blood (including PKs, biomarker and immunogenicity) and tissue specimens;
- Enrollment/randomization worksheets;
- Pregnancy Surveillance Forms;
- SAE reporting instructions and forms.

5.3 Safety Assessments

At baseline, a medical history will be obtained to capture relevant underlying conditions. Baseline signs and symptoms are those that are assessed within 2 weeks prior to treatment arm assignment. The baseline physical examination should include: weight, height, ECOG performance status, blood pressure, heart rate, electrocardiogram, O₂ saturation (pulse oximetry) and temperature; it should be performed within 28 days of treatment arm assignment. Concomitant medications will be collected from within 2 weeks prior to treatment arm assignment through the study treatment period (see [Table 5.1A](#), [Table 5.1B](#), [Table 5.1C](#), [Table 5.1D](#), and [Table 5.1E](#)).

Subjects will be considered evaluable for safety if they have received any study drug.

Toxicity assessments will be continuous during the treatment phase and follow-up phases.

Performance status and body weight should be assessed at each on study visit. Vital signs should also be taken as per institutional standard of care prior to, during and after the infusions with investigational products. Pulse oximetry should be done prior to each infusion as well. The start and stop time of the study drug infusion should be documented. If there are any new or worsening clinically significant changes since the last exam, report changes on the appropriate non-serious or serious adverse event page.

Additional measures including non-study required laboratory tests should be performed as clinically indicated.

Safety assessments will be based on the medical review of adverse event reports, results of vital sign measurements, Eastern Cooperative Oncology Group (ECOG) performance status, physical examinations, clinical laboratory results, ECGs, and imaging tests.

The incidence of observed adverse events will be categorized using the most current version of MedDRA and reviewed for potential significance and clinical importance. Adverse events will

be evaluated according to the National Cancer Institute Common Terminology Criteria for Adverse Events (NCI CTCAE) version 4.0.

5.3.1 Laboratory Test Assessments

Clinical laboratories will be assessed (see [Table 5.1A](#), [Table 5.1B](#), [Table 5.1C](#), [Table 5.1D](#), and [Table 5.1E](#)). Sites should collect screening samples between -14 to -3 days from assignment to insure that results required for eligibility purposes are verified prior to the assignment to study. Estimated GFR will be calculated by either Cockcroft-Gault, CKD-EPI, or MDRD, formulas from the supplied serum creatinine value supplied by the site. Pregnancy testing must be performed within 24 hours prior to the initial administration of investigational product at baseline and then within 24 hours of each study drug administration. CBC plus differential and serum chemistry panel should be drawn within 72 hours prior to each subsequent scheduled treatment. On study labs will be done on site/locally. Laboratory tests may be done more frequently if indicated. Additional laboratory tests should be performed as per standard of care.

Laboratory toxicities (eg, suspected drug induced liver enzyme elevations) will be monitored during the follow-up phase via on site/local labs until all study drug related toxicities resolve, return to baseline or are deemed irreversible.

The following clinical laboratory tests will be performed:

Hematology

WBC
Hemoglobin
Hematocrit
MCV
RDW
Differential Count
Platelet count

Serum Chemistry

Sodium
Potassium
Chloride
CO₂
Blood Urea Nitrogen (BUN) or serum urea level
Creatinine
Estimated GFR
Glucose
Calcium
Magnesium
Phosphorus
Aspartate Transaminase
Alanine Transaminase
Alkaline Phosphatase
Total Bilirubin

Direct Bilirubin
Albumin
Total Protein
Amylase
Lipase
Lactate Dehydrogenase

Serology (screening only)

Human immunodeficiency virus 1/2 antibody
Hepatitis B virus surface antigen
Hepatitis C antibody

Note: May obtain additional testing or substitute testing per institutional guidelines to rule out infection

Urine Studies (screening only)

Urinalysis (dipstick)

Other Assays

TSH (if TSH is abnormal then obtain free T3 and free T4)
Anti- thyroid antibodies (stimulating and anti-thyroperoxidase (TPO) at screening only)
Adenocorticotrophic hormone collected in the morning at screening, then as clinically indicated (if ACTH is abnormal then obtain cortisol)

Other Analyses

Pregnancy test (WOCBP only at screening and 24hrs prior study drug administration)
FSH (if needed to document post-menopausal status as defined in [Section 3.3.3](#))

At the investigator's discretion, laboratory tests may be repeated if clinically significant.

Results of all laboratory tests required by this protocol must be provided to BMS, either recorded on the laboratory pages of the CRF or by another mechanism as agreed upon between the investigator and BMS (eg, provided electronically). If the units of a test result differ from those printed on the CRF, the recorded laboratory values must specify the correct units. Any abnormal laboratory test result considered clinically significant by the investigator must be recorded on the appropriate AE page of the CRF (see [Section 6.2](#) Laboratory Test Abnormalities).

5.3.2 ECG Evaluation

Single 12-lead ECGs will be collected at screening and on study.

5.4 Efficacy Assessments

Disease evaluation with computed tomography (CT) and/or magnetic resonance imaging (MRI) of chest, abdomen, and pelvis, as appropriate, will be performed at baseline, and then

approximately every 8 weeks until confirmed disease progression as described in [Section 4.3.8](#) and/or completion of follow-up. Brain MRI will be performed at screening, approximately every 16 weeks thereafter, and if clinically indicated. Brain MRI will be performed approximately every 8 weeks for subjects in Arms D and E.

In the Extension Period, tumor assessments will be performed every 8 weeks (prior to dosing). CT Chest and CT or MRI abdomen, pelvis and all known sites of disease should be performed using the same imaging method used at screening. For Arms D and E only, MRI brain will also be performed (subjects in other arms who have stable brain metastases should have surveillance brain MRI approximately every 16 weeks and as clinically indicated).

Tumor response will be determined for all subjects as defined by RECIST 1.1. Individual patients will be treated according to principles that allow treatment beyond initial radiographic progression (outlined in [Section 4.3.8](#)).

At the sponsor's discretion, scans and measurements may be reviewed by independent radiologists using RECIST 1.1 criteria at a later date or any time during the study. In the absence of clinical deterioration, any initial assessment of progressive disease (PD) will be confirmed by a repeat evaluation at the next tumor assessment time point, but no sooner than 4 weeks later.

5.5 Pharmacokinetic Assessments

[Table 5.5A](#), [Table 5.5C](#), [Table 5.5D](#) and [Table 5.5E](#) list the sampling schedule to be followed for the assessment of pharmacokinetics. Blood samples should be drawn from a site other than the infusion site (ie, contralateral arm) on days of infusion. All samples collected pre-dose should be taken just prior to the administration, and end-of-infusion (EOI) samples should be taken as close to EOI as possible (preferably 2 minutes prior to EOI) on the contralateral arm (ie, the arm not for the infusion). **All other on-treatment timepoints are relative to the start of study drug administration; when both nivolumab and ipilimumab are administered on the same day, samples should be collected relative to the start of nivolumab infusion.** If the infusion was interrupted, the reason for interruption should also be documented on the CRF. Blood samples will be processed to collect serum. PK samples will be analyzed for nivolumab or ipilimumab by validated immunoassays. Additional exploratory analysis may be conducted; exploratory results will not be reported. Further details of blood collection, labeling, processing, storage and shipping will be provided to the site in the laboratory manual.

Table 5.5A: CA209038 Pharmacokinetic (PK), Pharmacodynamic, and Biomarker Sampling Schedule (Part 1, Cohorts 1 and 2)

Study Day	Time (Event)	Time (Relative to Start of Infusion) Hours:Min	PK Serum Sample	ADA	SNP& HLA/ KIR typing	Tumor Ag specific T-cells with a CBC and differential	PB Gene Expression Profiling	PBMC Flow Cytometry with a CBC and differential	Soluble Factors (Serum)	Anti-Tumor Antibodies	PBMC Functional Assays with a CBC and differential	Tumor Biopsy
Screening (day -7 to day1 pre-dose)					X	X	X	X	X	X	X	X (once eligibility determined)
Cycle1 Day 1	0 (predose)	00:00	X	X			X					
Cycle1 Day 1	1 (EOI)	01:00	X									
Cycle1 Day 1	3	03:00	X						X			
Cycle1 Day 1	7	07:00	X						X			
Cycle 1 Day 2	0	24:00	X				X		X			
Cycle 1 Day 3	0	48:00	X									
Cycle 1 Day 4	0	72:00	X					X ^a				
Cycle 1 Day 8	0	168:00	X				X	X ^a			X ^a	

Table 5.5A: CA209038 Pharmacokinetic (PK), Pharmacodynamic, and Biomarker Sampling Schedule (Part 1, Cohorts 1 and 2)

Study Day	Time (Event)	Time (Relative to Start of Infusion) Hours:Min	PK Serum Sample	ADA	SNP& HLA/ KIR typing	Tumor Ag specific T-cells with a CBC and differential	PB Gene Expression Profiling	PBMC Flow Cytometry with a CBC and differential	Soluble Factors (Serum)	Anti-Tumor Antibodies	PBMC Functional Assays with a CBC and differential	Tumor Biopsy
Cycle1 Day 15	0 (predose)	00:00	X	X				X	X		X	
Cycle 1 Day 29	0 (predose)	00:00	X			X	X	X	X	X	X	X (day 23 to day 29)
Cycle 1 Day 43	0 (predose)	00:00	X	X					X			
Cycle 1 Day 43	1 (EOI)	01:00	X									
Cycle2 Day1	0 (predose)	00:00	X	X		X	X	X		X	X	
Cycle 2 Day 29	0 (predose)	00:00	X									
Cycle 3 Day 15	0 (predose)	00:00	X	X								
Cycle 3 Day 15	1 (EOI)	01:00	X									
Cycle 5 Day 1 (Every 16 weeks after Cycle 3)	0 (predose)	00:00	X	X								

Table 5.5A: CA209038 Pharmacokinetic (PK), Pharmacodynamic, and Biomarker Sampling Schedule (Part 1, Cohorts 1 and 2)

Study Day	Time (Event)	Time (Relative to Start of Infusion) Hours:Min	PK Serum Sample	ADA	SNP& HLA/ KIR typing	Tumor Ag specific T-cells with a CBC and differential	PB Gene Expression Profiling	PBMC Flow Cytometry with a CBC and differential	Soluble Factors (Serum)	Anti-Tumor Antibodies	PBMC Functional Assays with a CBC and differential	Tumor Biopsy
Follow-up Visit 1 (40-60 days after last treatment)			X	X								
Follow-up Visit 2 (101-120 days since last treatment)			X	X								

^a CBCs required will be done locally and not by central lab

Table 5.5B: CA209038 Pharmacodynamic and Biomarker Sampling Schedule (Parts 2, 3 and 4, Arms A, B, D and E)

Study Day	Time (Event)	Time (Relative to Start of Infusion) Hours:Min	SNP& HLA/ KIR typing	Tumor Ag specific T-cells with a CBC and differential	MDSCs	PB Gene Expression Profiling	PBMC Flow Cytometry with a CBC and differential	Soluble Factors (Serum)	Anti-Tumor Antibodies	PBMC Functional Assays with a CBC and differential	Tumor Biopsy
Screening			X	X ^a	X	X	X ^a	X	X	X ^a	X ^{b,c}
Week 1 Day 1	0 (predose)	00:00				X					
Week 1 Day 1	3 h	03:00						X			
Week 1 Day 1	7 h	07:00						X			
Week 1 Day 2	0	24:00				X		X			
Week 1 Day 3	0	48:00						X			
Week 1 Day 4	0	72:00					X ^a	X			
Week 2 Day 1	0	168:00				X	X ^a	X		X ^a	X (+7 days) ^{c,d}

Table 5.5B: CA209038 Pharmacodynamic and Biomarker Sampling Schedule (Parts 2, 3 and 4, Arms A, B, D and E)

Study Day	Time (Event)	Time (Relative to Start of Infusion) Hours:Min	SNP& HLA/ KIR typing	Tumor Ag specific T-cells with a CBC and differential	MDSCs	PB Gene Expression Profiling	PBMC Flow Cytometry with a CBC and differential	Soluble Factors (Serum)	Anti-Tumor Antibodies	PBMC Functional Assays with a CBC and differential	Tumor Biopsy
Week 3 Day 1	0 (predose)	00:00				X	X ^a	X		X ^a	
Week 4 Day 1	0 (predose)					X	X ^a	X		X ^a	X (+7 days after 2nd dose) ^{c,e}
Week 5 Day 1	0 (predose)	00:00		X ^a		X	X ^a	X		X ^a	
Week 7 Day 1	0 (predose)	00:00			X	X	X ^a	X	X	X ^a	
Week 13 Day 1	0 (predose)	00:00		X ^a			X ^a		X	X ^a	
Follow-up Visit 1 (40-60 days after last treatment)											X - obtain upon progression ^f
Follow-up Visit 2 (101-120 days after last treatment)											X - obtain upon progression ^f

Table 5.5B: CA209038 Pharmacodynamic and Biomarker Sampling Schedule (Parts 2, 3 and 4, Arms A, B, D and E)

Study Day	Time (Event)	Time (Relative to Start of Infusion) Hours:Min	SNP& HLA/ KIR typing	Tumor Ag specific T-cells with a CBC and differential	MDSCs	PB Gene Expression Profiling	PBMC Flow Cytometry with a CBC and differential	Soluble Factors (Serum)	Anti-Tumor Antibodies	PBMC Functional Assays with a CBC and differential	Tumor Biopsy
Upon occurrence of \geq Grade 3/4 drug-related AE								X			
Local surgery of isolated symptomatic lesions (see Section 3.4.1)											X ^f
Re-treatment after interrupted active treatment											X ^f

^a CBCs required will be done locally and not by central lab

^b Must contain sufficient tumor content (\geq 100 tumor cells in a 4 micron section) upon central pathology assessment;

^c Biopsy is strongly encouraged but not mandatory in Part 4

^d On-treatment biopsy window for Part 2, group 1 biopsy is Week 2, Day 1+7 days; potential on-treatment biopsy window for Parts 3 and 4, if determined to be optimal biopsy window.

^e On-treatment biopsy window for Part 2, group 2 is Week 4, Day 1+7 days; potential on-treatment biopsy window for Parts 3 and 4, if determined to be optimal biopsy window.

^f Biopsy is strongly encouraged but not mandatory. May be done at either Follow-up visit 1 or Follow-up visit 2

Table 5.5C: PK and ADA Sampling Schedule - Part 2 Arm A

Study Day	Time (Event)	Time (Relative to Start of Nivolumab Infusion) Hours Min ^a	PK Serum Sample Nivolumab	Immuogenicity Sample Nivolumab	PK Serum Sample Ipilimumab	Immunogenicity Sample Ipilimumab
Week 1 Day 1	0 (predose)	00:00	X	X	X	X
Week 1 Day 1	1 h (EOI-Nivo)	01:00	X			
Week 1 Day 1	3 h (EOI-Ipi)	03:00	X		X	
Week 1 Day 1		07:00	X		X	
Week 1 Day 2		24:00	X		X	
Week 1 Day 3		48:00	X		X	
Week 1 Day 4		72:00	X		X	
Week 2 Day 1		168:00	X		X	
Week 4 Day 1	0 (predose)	00:00	X	X	X	X
Week 7 Day 1	0 (predose)	00:00	X	X	X	X
Week 7 Day 1	1 h (EOI-Nivo)	01:00	X			
Week 7 Day 1	3 h (EOI-Ipi)	03:00			X	
Week 10 Day 1	0 (predose)	00:00	X	X	X	X
Week 13 Day 1	0 (predose)	00:00	X	X	X	
Week 13 Day 1	1 h (EOI-Nivo)	01:00	X			
Week 25 Day 1	0 (predose)	00:00	X	X	X	X

Table 5.5C: PK and ADA Sampling Schedule - Part 2 Arm A

Study Day	Time (Event)	Time (Relative to Start of Nivolumab Infusion) Hours Min ^a	PK Serum Sample Nivolumab	Immuogenicity Sample Nivolumab	PK Serum Sample Ipilimumab	Immunogenicity Sample Ipilimumab
Week 53 Day 1	0 (predose)	00:00	X	X	X	X
Week 79 Day 1	0 (predose)	00:00	X	X		
Week 95 Day 1	0 (predose)	00:00	X	X		
Follow-up Visit 1 (40-60 days after last treatment)			X	X	X ^b	X ^b
Follow-up Visit 2 (101-120 days since last treatment)			X	X	X ^b	X ^b

^a All samples should be timed relative to the **start of nivolumab** infusion, except for the ipilimumab end of infusion (EOI) samples which are to be taken just prior to the end of the ipilimumab infusion.

^b Ipilimumab Follow up PK and immunogenicity samples collected only if subject discontinues treatment before Week 25.

Table 5.5D: PK and ADA Sampling Schedule Part 3 and Part 4, Arm B and E

Study Day	Time (Event)	Time (Relative to Start of Infusion) Hours:Min	PK Serum Sample Nivolumab	Immunogenicity Sample Nivolumab
Week 1 Day 1	0 (predose)	00:00	X	X
Week 1 Day 1	0.5 (EOI)	00:30	X	
Week 1 Day 1		03:00	X	
Week 1 Day 1		07:00	X	
Week 1 Day 2		24:00	X	
Week 1 Day 3		48:00	X	
Week 1 Day 4		72:00	X	
Week 2 Day 1		168:00	X	
Week 3 Day 1	0 (predose)	00:00	X	X
Week 5 Day 1	0 (predose)	00:00	X	
Week 7 Day 1	0 (predose)	00:00	X	X
Week 7 Day 1	0.5 h (EOI)	00:30	X	
Week 13 Day 1	0 (predose)	00:00	X	X
Week 13 Day 1	0.5 h (EOI)	00:30	X	
Week 25 Day 1	0 (predose)	00:00	X	X
Week 53 Day 1	0 (predose)	00:00	X	X
Week 79 Day 1	0 (predose)	00:00	X	X

Table 5.5D: PK and ADA Sampling Schedule Part 3 and Part 4, Arm B and E

Study Day	Time (Event)	Time (Relative to Start of Infusion) Hours:Min	PK Serum Sample Nivolumab	Immunogenicity Sample Nivolumab
Week 95 Day 1	0 (predose)	00:00	X	X
Follow-up Visit 1 (40-60 days after last treatment)			X	X
Follow-up Visit 2 (101-120 days since last treatment)			X	X

Table 5.5E: PK and ADA Sampling Schedule - Parts 3 and 4 Arm A and D

Study Day	Time (Event)	Time (Relative to Start of Nivolumab Infusion) Hours Min ^a	PK Serum Sample Nivolumab	Immuogenicity Sample Nivolumab	PK Serum Sample Ipilimumab	Immunogenicity Sample Ipilimumab
Week 1 Day 1	0 (predose)	00:00	X	X	X	X
Week 1 Day 1	0.5 h (EOI-Nivo)	00:30	X			
Week 1 Day 1	1.5 h (EOI-Ipi)	01:30	X		X	
Week 1 Day 1		07:00	X		X	
Week 1 Day 2		24:00	X		X	
Week 1 Day 3		48:00	X		X	
Week 1 Day 4		72:00	X		X	
Week 2 Day 1		168:00	X		X	
Week 4 Day 1	0 (predose)	00:00	X	X	X	X
Week 7 Day 1	0 (predose)	00:00	X	X	X	X
Week 7 Day 1	0.5 h (EOI-Nivo)	00:30	X			
Week 7 Day 1	1.5 h (EOI-Ipi)	01:30			X	
Week 10 Day 1	0 (predose)	00:00	X	X	X	X
Week 13 Day 1	0 (predose)	00:00	X	X	X	
Week 13 Day 1	0.5 h (EOI-Nivo)	00:30	X			
Week 25 Day 1	0 (predose)	00:00	X	X	X	X

Table 5.5E: PK and ADA Sampling Schedule - Parts 3 and 4 Arm A and D

Study Day	Time (Event)	Time (Relative to Start of Nivolumab Infusion) Hours Min ^a	PK Serum Sample Nivolumab	Immuogenicity Sample Nivolumab	PK Serum Sample Ipilimumab	Immunogenicity Sample Ipilimumab
Week 53 Day 1	0 (predose)	00:00	X	X	X	X
Week 79 Day 1	0 (predose)	00:00	X	X		
Week 95 Day1	0 (predose)	00:00	X	X		
Follow-up Visit 1 (40-60 days after last treatment)			X	X	X ^b	X ^b
Follow-up Visit 2 (101-120 days since last treatment)			X	X	X ^b	X ^b

^a All samples should be timed relative to the **start of nivolumab** infusion, except for the ipilimumab end of infusion (EOI) samples which are to be taken just prior to the end of the ipilimumab infusion.

^b Ipilimumab Follow up PK and immunogenicity samples collected only if subject discontinues treatment before Week 25.

[REDACTED]

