3 INVESTIGATIONAL PLAN

3.1 Study Design and Duration

Study Design: This is an exploratory, open-label, multicenter study of nivolumab and nivolumab in combination with ipilimumab.

Approximately 150 subjects with advanced melanoma (unresectable or metastatic) will be treated in this study in four (4) parts. Part 1 of this study will have two (2) cohorts consisting of approximately 40 patients each: cohort 1 will consist of anti-CTLA4 therapy-naïve patients and cohort 2 will consist of patients who have progressed on an anti-CTLA-4 regimen. Cohorts 1 and 2 will be administered nivolumab at 3 mg/kg dose level every 2 weeks. Subjects will go through a **screening period** of no longer than 28 days and eligible subjects will start the **treatment period** for a duration of 2 years depending on their response. Nivolumab will be administered by IV infusion every 14 days in 56 day cycles (on days 1, 15, 29 and 43 of each cycle). Response assessments will be performed on days 49-56. The response assessment must be completed before the first dose in the next cycle.

In Part 2, approximately 20 anti-CTLA4 therapy-naïve patients will be administered nivolumab at 1 mg/kg and ipilimumab at 3 mg/kg every 3 weeks for 4 doses, followed by nivolumab 3 mg/kg alone every 2 weeks (Arm A). This part of the study is aimed at defining the optimal window for on-treatment biopsy with concurrent nivolumab and ipilimumab therapy. All subjects will be required to undergo a pre-treatment biopsy and consent to on-treatment biopsy. Two (2) groups of approximately 10 patients each will be enrolled sequentially with the first group assigned to an on-treatment biopsy between Days 8 and 15 (weeks 2 and 3) after the start of therapy and the second group assigned to an on-treatment biopsy between Days 22 and 29 (subsequent to the second dose of therapy between weeks 4 and 5) after the start of therapy. Optimal biopsy timing will be defined as the biopsy window with the greatest pharmacodynamic

increase in intratumoral activated T cells compared to the pre-treatment biopsy. The defined optimal on-treatment biopsy window will be used in the third part of this study.

In Part 3, approximately 30 anti-CTLA4 therapy-naive patients will be randomized 2:1 and treated with one of the following:

- Arm A: nivolumab 1 mg/kg IV combined with ipilimumab 3 mg/kg IV Q3W for 4 doses then nivolumab 3 mg/kg IV Q2W
- Arm B: nivolumab 3 mg/kg IV Q2W

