4.1 Study Treatments

Treatment administration for nivolumab and ipilimumab (a ± 2 -day window will be allowed):

Table 4.1-1: Treatment Administration

Cohort/Arm	Dose	Infusion Time
1 and 2	3 mg/kg nivolumab every 2 weeks	60 minutes
A	1 mg/kg nivolumab + 3 mg/kg ipilimumab every 3 weeks x 4 doses and then 3 mg/kg nivolumab every 2 weeks	Part 2: nivolumab 60 minutes + 30 minutes break ipilimumab 90 minutes and then nivolumab 60 minutes
		Part 3: nivolumab 30 minutes + 30 minutes break ipilimumab 30 minutes and then nivolumab 30 minutes
B	3 mg/kg nivolumab every 2 weeks	30 minutes
D	1 mg/kg nivolumab + 3 mg/kg ipilimumab every 3 weeks x 4 doses and then 3 mg/kg nivolumab every 2 weeks	nivolumab 30 minutes + 30 minutes break ipilimumab 30 minutes and then nivolumab 30 minutes
E	3 mg/kg nivolumab every 2 weeks	30 minutes

Table 4.1-2: Product Description

Product Description and Dosage Form	Potency	Primary Packaging (Volume)/ Label Type	Secondary Packaging (Qty) /Label Type	Appearance	Storage Conditions (per label)
BMS-936558-01 Solution for Injection	100 mg (10mg/mL)	10 mL/ open label	10 vials per box/ open labels	Colorless to pale yellow, clear to opalescent solution; may contain particles	Store Refrigerated, 2-8° C (36-46 F) Protect from light and freezing.
Ipilimumab Solution for Injection	200 mg (5 mg/mL)	40 mL per vial/Open- label	4 vials per carton/Open-label	Clear, colorless to pale yellow liquid. May contain particles	2 to 8°C. Protect from light and freezing.

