2 STUDY DESCRIPTION

2.1 Study Design

This is an exploratory, open-label, multicenter study of nivolumab and nivolumab in combination with ipilimumab.

Approximately 150 subjects with advanced melanoma (unresectable or metastatic) will be treated in this study in four (4) parts.

Part 1 of this study will have two (2) cohorts consisting of approximately 40 patients each: cohort 1 will consist of anti-CTLA4 therapy-naive patients and cohort 2 will consist of patients who have progressed on an anti-CTLA-4 regimen. Cohorts 1 and 2 will be administered nivolumab at 3 mg/kg dose level every 2 weeks. Subjects will go through a screening period of no longer than 28 days and eligible subjects will start the treatment period for a duration of 2 years depending on their response. Nivolumab will be administered by IV infusion every 14 days in 56 day cycles (on days 1, 15, 29 and 43 of each cycle). Response assessments will be performed on days 49-56. The response assessment must be completed before the first dose in the next cycle.

In Part 2, approximately 20 anti-CTLA4 therapy-naive patients will be administered nivolumab at 1 mg/kg and ipilimumab at 3 mg/kg every 3 weeks for 4 doses, followed by nivolumab 3 mg/kg alone every 2 weeks (Arm A). This part of the study is aimed at defining the optimal window for on-treatment biopsy with concurrent nivolumab and ipilimumab therapy. All subjects will be required to undergo a pre-treatment biopsy and consent to on-treatment biopsy. Two (2) groups of approximately 10 patients each will be enrolled sequentially with the first group assigned to an on-treatment biopsy between Days 8 and 15 (weeks 2 and 3) after the start of therapy and the second group assigned to an on-treatment biopsy between Days 22 and 29 (subsequent to the second dose of therapy between weeks 4 and 5) after the start of therapy. Optimal biopsy timing will be defined as the biopsy window with the greatest pharmacodynamic increase in intratumoral activated T cells compared to the pre-treatment biopsy. The defined optimal on-treatment biopsy window will be used in the third part of this study.

In Part 3, approximately 30 anti-CTLA4 therapy-naive patients will be randomized 2:1 and treated with one of the following:

- Arm A: nivolumab 1 mg/kg IV combined with ipilimumab 3 mg/kg IV Q3W for 4 doses then nivolumab 3 mg/kg IV Q2W
- Arm B: nivolumab 3 mg/kg IV Q2W

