6.3 Populations for Analyses

- All Enrolled Subjects: All subjects who signed an informed consent form and were registered into the IVRS.
- All Treated Subjects: All subjects who received at least one dose of study medication
- Pharmacokinetic Subjects: All subjects who received at least one dose of study medication and have available serum concentration data
- Response Evaluable Subjects: All treated subjects with measurable disease at baseline and one of the following: 1) at least one post-baseline tumor assessment, 2) clinical progression, or 3) death (if death occurred within 100 days after last dose of study medication)
- Immunogenicity Subjects:
 - Nivolumab ADA Evaluable Subjects: All treated subjects with baseline and at least 1 post-baseline nivolumab immunogenicity assessment.
 - Ipilimumab ADA Evaluable Subjects: All treated subjects with baseline and at least 1 post-baseline ipilimumab immunogenicity assessment.
- Biomarker Evaluable Subjects: All Treated Subjects with at least one evaluable measurement for a specific marker will be included in the dataset for that marker. Evaluable may differ depending on the analysis.

Table 6.2-1: Treatment Administration

Cohort/ Arm	Dose	Infusion Time	Population
1 and 2	3 mg/kg nivolumab every 2 weeks	60 minutes	Cohort 1: ~40 anti-CTLA4 naive subjects Cohort 2: ~40 anti-CTLA4 progressed subjects
A	1 mg/kg nivolumab + 3 mg/kg ipilimumab every 3 weeks x 4 doses And then 3 mg/kg nivolumab	Part 2: nivolumab 60 minutes + 30 minutes break + ipilimumab 90 minutes And then nivolumab 60	Anti-CTLA4 naive only ~10 subjects with biopsy window between Days 8 and 15 ~10 subjects with biopsy

Table 6.2-1: Treatment Administration

Cohort/ Arm	Dose	Infusion Time	Population
	every 2 weeks	minutes Part 3: nivolumab 30 minutes + 30 minutes break + ipilimumab 30 minutes And then nivolumab 30 minutes	window between Days 22 and 29 Anti-CTLA4 naive only ~20 reduced infusion subjects
B	3 mg/kg nivolumab every 2 weeks	30 minutes	Anti-CTLA4 naive only ~10 reduced infusion subjects
D	1 mg/kg nivolumab + 3 mg/kg ipilimumab every 3 weeks x 4 doses And then 3 mg/kg nivolumab every 2 weeks	Nivolumab 30 minutes + 30 minutes break + ipilimumab 30 minutes And then nivolumab 30 minutes	Anti-CTLA4 naive only ~10 reduced infusion subjects with brain metastases
E	3 mg/kg nivolumab every 2 weeks	30 minutes	Anti-CTLA4 naive only ~10 reduced infusion subjects with brain metastases

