 - In the event that this occurs, this will be treated as subject's subsequent therapy for certain efficacy assessments described in [Section 4.2.2](#).
- Subjects receiving treatment that is different than what they were assigned or randomized

- In the event that this occurs, subjects will be grouped with the actual received treatment (instead of assigned or randomized treatment) for the analyses.
- For Part 2, subjects whose on-treatment biopsy day relative to the start of study therapy is considerably different than the biopsy window which they were assigned.
 - In the event that this occurs, subjects would be grouped with their actual biopsy window (instead of assigned), or they would be excluded from the grouping schemes comparing the biopsy windows if their on-treatment biopsy is outside the 2 allowable windows.
- During the first dosing visit, if subjects receive ipilimumab dose first, before receiving the nivolumab dose during a visit which a combination therapy is planned.
- Subjects receiving immunosuppressive agents during the course of treatment on or prior to Cycle 2 Day 1 for Part 1 subjects and Week 13 Day 1 for Part 2-4 subjects.
 - In the event that this occurs, pharmacodynamic biomarker analyses may be repeated, as a sensitivity analysis, without these subjects or excluding data points after initiation of immunosuppressive agents.

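### The late biopsy window is anchored to the second dose in one place and to study days in others, and the SAP's Part 2 grouping rule never checks whether dose 2 was given

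*Protocol*

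**What the plan says.** The late window is described in three ways.

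- **Dose anchor.** In Protocol Table 5.5B, which covers Arms A, B, D and E, the late biopsy cell reads "7 days after 2nd dose", with a plus sign in front.
- **Calendar anchor.** That cell sits in the Week 4 Day 1 row, and footnote e restates it: "On-treatment biopsy window for Part 2, group 2 is Week 4, Day 1+7 days; potential on-treatment biopsy window for Parts 3 and 4", if that window proves optimal. SAP Table 6.2-1 describes the second Part 2 group by a biopsy "window between Days 22 and 29", with no mention of a dose.
- **Both conditions.** Protocol 3.1 places the biopsy "between Days 22 and 29 (subsequent to the second dose of therapy between weeks 4 and 5". SAP 2.1 repeats this: "on-treatment biopsy between Days 22 and 29 (subsequent to the second dose of therapy between weeks 4 and 5".

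Three other provisions matter. Protocol 4.1 gives dosing a tolerance of 2 days either side ("day window will be allowed"). Protocol 4.3.9 moves a visit's procedures along with an infusion that is 1 to 7 days late, treats a longer delay as a missed dose, and times later visits from the last actual dose. SAP 7.2.3 judges Part 2 biopsy timing by the day relative to start of therapy. When that day is considerably off the assigned window, "subjects would be grouped with their actual biopsy window (instead of assigned"; biopsies outside both windows leave the comparison of windows.

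**The concern.** Part 2 exists to choose between an early window after one combination dose and a late window after two, using two groups of about 10. The chosen window then fixes sampling in Part 3. It also defines the Arm A precision statement, which rests on 30 subjects biopsied in the optimal window (about 10 from the chosen Part 2 group plus about 20 from Part 3). T cell infiltration in tumour tissue is one of the primary endpoints in SAP Table 4.1-1.

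If the late group is defined by study day alone, it can include tissue taken after a single dose and lose tissue taken properly after two. If the late window is carried into Part 3, the table cell can also be read so that Arm B is biopsied about a week before Arm A. The two arms would then differ in sampling time as well as in treatment.

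**Working it through.** **Conversion.** Study day = 7 × (week − 1) + day. Week 2 Day 1 is Day 8, and adding 7 gives Day 15. Week 4 Day 1 is 7 × 3 + 1 = Day 22, and adding 7 gives Day 29. The plan's two windows, Days 8-15 and Days 22-29, are reproduced.

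**Nominal dosing.** Three-weekly: dose 2 on Day 1 + 21 = Day 22. Two-weekly: dose 2 on Day 1 + 14 = Day 15 and dose 3 on Day 29.

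**Comparison.** The dose-anchored window, read as a range, is dose 2 to dose 2 + 7 days. The calendar window is Days 22-29, which is 8 days. Whole days are counted, and the day of dosing is treated as after the dose.

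| Schedule and day of dose 2 | Dose-anchored window | Shared with Days 22-29 | Days in 22-29 that precede dose 2 |
|---|---|---|---|
| Three-weekly, 2 days early (Day 20) | 20-27 | 22-27 (6 days) | none |
| Three-weekly, on time (Day 22) | 22-29 | all 8 days | none |
| Three-weekly, 2 days late (Day 24) | 24-31 | 24-29 (6 days) | 22-23 |
| Three-weekly, 7 days late (Day 29) | 29-36 | Day 29 only | 22-28 |
| Three-weekly, 8 days late (Day 30) | 30-37 | none | 22-29 |
| Two-weekly, on time (Day 15) | 15-22 | Day 22 only | none |
| Two-weekly, 2 days late (Day 17) | 17-24 | 22-24 (3 days) | none |

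**Part 2, Arm A, under SAP 7.2.3.** Take dose 2 on Day 29.

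- A biopsy on Day 25, before that dose, breaches the protocol text. Its day from start of therapy is still inside Days 22-29, so the SAP rule leaves it in the late group, although it is tissue 24 days after a single dose.
- A biopsy on Day 34 is 5 days after dose 2 and fits the table cell. It also follows from Protocol 4.3.9, which moves the visit procedures with the dose. Counted from start of therapy it lies outside both windows, so it can be excluded.
- If dose 2 is on Day 24 and the biopsy falls on Days 24-29, every definition is met and nothing changes.

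One affected subject in a group of about 10 is 1/10 = 10% of that group.

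**Part 3, Arm B, if the late window is chosen.** Under the cell read as a range, an on-schedule subject is biopsied 0 to 7 days after dose 2 (Days 15-22). Under footnote e it is 22 − 15 = 7 to 29 − 15 = 14 days after dose 2, with dose 3 due on the last day. Every day in either range follows dose 2. If the cell instead means exactly 7 days after dose 2, it points to Day 22, which lies in both. For comparison, Part 1 Cohort 1, on the same two-weekly dose, is biopsied "day 23 to day 29"; the range Days 15-22 does not meet that window at all.

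**The case against.** The best defence is that the intent is clear. The protocol text and SAP 2.1 both tie the late biopsy to the second dose, and every description gives Days 22-29 after dose 2 for three-weekly subjects on schedule. Protocol 4.3.9 moves procedures with a short delay. SAP 7.2.3 acts only on considerable departures and speaks of the actual window, which SAP 2.1 describes with the dose condition. This stands for the on-schedule case. It does not settle the late-dose case, because the stated trigger in SAP 7.2.3 is the day from start of therapy. A biopsy on Days 22-29 before dose 2 does not depart from the window on that measure and would not be flagged.

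The two-weekly problem is conditional. Part 2 has no two-weekly arm, the late window reaches Arm B only if chosen, and Part 4 biopsies are optional. It therefore bears mainly on about 10 Arm B subjects. That limits its reach but does not remove the ambiguity. Protocol Section 5.6, to which Table 5.1A refers for tumour tissue, is blacked out and may state the anchor, so the finding rests on the visible text.

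The documents do not support some stronger inferences that a reader might draw:

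- That the text and SAP use study days alone. Protocol 3.1 and SAP 2.1 also carry the dose condition.
- That the 2-day dosing tolerance allows a biopsy before dose 2 without a deviation. The text and the table cell both place the biopsy after dose 2.
- That on-schedule two-weekly subjects yield a mix of one-dose and two-dose tissue. Both readings follow dose 2.

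**Conclusion.** The inconsistency is real and worth correcting before Part 2 is analysed. The more consequential part is SAP 7.2.3, which can keep one-dose tissue in the late group and exclude tissue correctly obtained after a delayed second dose. Each instance moves about 10% of a group of 10 in the comparison that selects the window.

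The number of instances cannot be derived, because no rate of late second doses is given. Purely as an assumption, 10-30% late would be 1 to 3 subjects in 10. It would be wrong to read these as 1 to 3 misgrouped, since a late dose matters only if the biopsy comes before it or falls after Day 29. Nor do the documents show that misgrouping would pull the two windows together, or that it would change the choice.

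The Arm B point is secondary. It depends on the late window being chosen and on the cell being read as a range. Its effect would be a different lag after dose 2 (0-7 against 7-14 days) and possibly different sampling times in Arms A and B.

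**What to change.** 1. Reconcile the Table 5.5B cell, footnote e, SAP Table 6.2-1 and SAP 7.2.3 to one stated anchor. State the intended study days for the two-weekly arms explicitly, so that Arms A and B are sampled on a comparable basis if the late window is carried forward.
2. In SAP 7.2.3, classify Part 2 biopsies by the number of combination doses received before the biopsy and the days since the last one. On the planned schedule the early window is one dose and 7-14 days since it (Days 8-15 less Day 1); the late window is two doses and 0-7 days since the second. Do not count a biopsy before dose 2 as late window, and do not exclude one taken 0-7 days after a delayed dose 2.

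The cost is a table cell, a footnote, a table entry and a few sentences in the SAP. No biopsy is added, dosing is untouched, and the rule needs only dose and biopsy dates. There are two small downsides. A few late-window biopsies will fall after Day 29, so calendar time varies slightly more. A Day 22-29 biopsy taken before dose 2 (21-28 days after dose 1) will belong to neither window and should be listed separately.
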